### 10.4 Subgroup analyses

Not applicable

### 10.5 Adjusted analysis

Not applicable

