#### 3.5 Secondary endpoints/outcomes

- All in-patient infections within 30 days of operation
- All in-patient antimicrobial consumption within 30 days of operation.
- Length of hospital stay after operation
- Mortality after operation at one year.
- Anastomotic leak within 30 days of operation
- Quality of life scores pre-operatively and at 30 days.
- Cost of healthcare treatments after operation at 30 days.

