### 7.3 The randomisation scheme

Simple randomisation with a 1:1 allocation ratio will be used to allocate patients.

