## 7.7 Trial assessments

### Pre-operative assessment-Visit 1

- Medical history
- Antibiotic history

Colo-Pro Pilot

- Rectal swab
- QofL assessment

#### Intra-operative assessment-Visit 2

- Anaesthetic history
- Surgical history
- Antibiotic prophylaxis history
- Antibiotic blood concentrations

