#### Post-operative assessment-Visit 5, day 30-45 post-operation

- This will normally be completed by postal or telephone assessment though when possible the 30-day follow-up might be combined with a patients post-operative clinic follow-up.
- Surgical site infection questionnaire relating to outpatient SSIs
- Antibiotic history
- QofL questionnaire

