**CONSORT 2010 Flow Diagram**

### 10.3.2 Primary outcome analysis

Statistical analyses of the primary outcome:

- Surgical site infection within 30 days of colorectal surgery will be analysed by comparing proportions.

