### 10.3.3 Secondary outcome analysis

Secondary outcomes will be analysed by comparing proportions.

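### Pre-operative EQ-5D is collected but has no role in the treatment comparison, and a score is to be analysed as a proportion; ANCOVA on the baseline score would gain precision with no new data

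*Combined protocol and SAP*

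**What the plan says.** Quality of life is a secondary endpoint, defined in section 3.5 as "Quality of life scores pre-operatively and at 30 days"; the Trial Summary also names both time points. Section 7.7 schedules a "QofL assessment" at the pre-operative visit and a "QofL questionnaire" at Visit 5, between day 30 and day 45. Section 11.1 identifies the instrument as EQ-5D.

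The analysis text is short. For the primary outcome, section 10.3.2 states: "Surgical site infection within 30 days of colorectal surgery will be analysed by comparing proportions". For everything else, section 10.3.3 states: "Secondary outcomes will be analysed by comparing proportions". The entry under "10.5 Adjusted analysis" is "Not applicable". Section 10.9 adds no further statistical considerations, and section 10.8 plans nothing for missing data beyond efforts to maximise follow-up.

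On allocation, section 7.3 states: "Simple randomisation with a 1:1 allocation ratio will be used to allocate patients". No stratification or minimisation is described.

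**The concern.** Two things do not fit together. First, the endpoint is worded as scores at two time points, but the only analysis offered is a comparison of proportions. No threshold or definition of improvement says how a score becomes a proportion. Second, the pre-operative score is collected from every patient, and nothing says how it enters the comparison between arms. It is not among the baseline variables listed in section 10.3.1 either.

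A patient's own baseline is usually the best available predictor of the later score. Leaving it out gives a wider interval than the data allow. Leaving its use unstated means the analyst must choose among a day-30 comparison, a change score, a dichotomy and an adjusted comparison after the data are in. Neither affects the validity of a randomised comparison, but both can be removed at almost no cost.

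**Working it through.** **Inputs from the documents.** The pilot has 90 patients allocated 1:1, so about 45 per arm. Section 10.1 bases the 90 on needing 60 patients with blood samples when about 30% cannot be sampled: 60/(1 - 0.30) = 85.7, so 86, and 90 x 0.70 = 63, which meets the need. The figure is thus a round-up for pharmacokinetics and was not set for EQ-5D precision. The plan gives no EQ-5D figure to reproduce: no standard deviation, no target difference and no correlation.

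**Assumptions.** The correlation r between pre-operative and day-30 EQ-5D is taken as 0.3, 0.5 or 0.7. The SD is taken as equal at the two time points, and both scores as available in all 90 patients. The small cost of estimating the regression slope is ignored.

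**Relative variance of the between-arm difference** (day-30 mean comparison = 1):

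| r | Day-30 only | Change score, 2(1 - r) | ANCOVA, 1 - r² |
|---|---|---|---|
| 0.3 | 1.00 | 1.40 | 0.91 |
| 0.5 | 1.00 | 1.00 | 0.75 |
| 0.7 | 1.00 | 0.60 | 0.51 |

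**Gain against day-30 only.** The variance falls by r² = 9%, 25% or 49%. The equivalent sample size is 90/(1 - r²): 90/0.91 = 99, 90/0.75 = 120, 90/0.51 = 176.

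**Gain against a change score.** The ratio is (1 - r²)/[2(1 - r)] = (1 + r)/2 = 0.65, 0.75 or 0.85, so the variance falls by 35%, 25% or 15%. At r = 0.3 a change score is worse than ignoring the baseline (1.40 against 1.00).

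**Detectable difference.** The illustration uses 80% power and two-sided 5%. With 45 per arm, the standard error in SD units is sqrt(2/45) = 0.211, and (1.96 + 0.84) x 0.211 = 0.59 SD for day-30 only. Multiplying by sqrt(1 - r²) gives 0.56, 0.51 or 0.42 SD.

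**Chance difference in baseline EQ-5D.** With the same standard error of 0.211 SD, a gap of at least 0.2 SD between arms has z = 0.2/0.211 = 0.95, a two-sided probability of 0.34. ANCOVA allows for such a gap; a day-30-only comparison does not.

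**Whether the same argument carries to surgical site infection (SSI).** Expected events at the section 10.1 rates are 45 x 0.165 + 45 x 0.0825 = 11.1. The standard error of the risk difference is sqrt(0.165 x 0.835/45 + 0.0825 x 0.9175/45) = 6.9 percentage points. Suppose a risk factor is present in 30% of patients (assumed), with SSI rates of 30% and 16.5% with and without it. The SD of its chance imbalance is sqrt(0.3 x 0.7 x 4/90) = 9.7 points, which shifts the risk difference by 0.097 x 13.5 = 1.3 points. That is 1.3/6.9 = 0.19 of a standard error, or about 3.6% of the variance.

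**The case against.** The strongest reply on EQ-5D is that the endpoint names the pre-operative score, so a comparison based on change may be intended. The plan would then not be ignoring the baseline. This is fair as far as it goes: the documents nowhere state a day-30-only comparison, so the gains of 9%, 25% and 49% are measured against an analysis the plan does not explicitly specify. But change is not specified either, and section 10.3.3 points to proportions. ANCOVA is more precise than both alternatives across the range shown, so the recommendation does not depend on which one was meant.

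It can also be said that this is a pilot sized for pharmacokinetic samples, that EQ-5D is one of several secondary outcomes, and that an unadjusted analysis is legitimate. All of that stands. It limits the weight of the point without removing it, because the change costs only wording.

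A reader might go further and infer from "Not applicable" and the unstratified allocation that every estimate, SSI included, is left distorted by chance imbalance, and that the SSI comparison should be stratified by a risk index such as the NNIS score. The documents do not support this. Chance imbalance under randomisation is not bias, and the unadjusted confidence interval already allows for it. The shift worked out above is under one fifth of a standard error and rests on assumed inputs. The 30% rate is the one section 2 gives for emergency surgery, and the documents give no SSI rate by NNIS score and no low/high cut. Those inputs also imply an overall rate of 0.3 x 30% + 0.7 x 16.5% = 20.6%, which does not match the 16.5% behind the 11 expected events. Nor does a plan with no adjusted analysis necessarily invite post-hoc adjustment: it fixes the unadjusted result, and a later adjusted one would be a visible departure.

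**Conclusion.** The point holds for EQ-5D. Sections 10.3.3 and 10.5, read together, give the pre-operative score no role in the treatment comparison and call for a score to be analysed as a proportion without saying how. The consequence is lost precision and an analysis left open, not an invalid result. The size depends on a correlation that the documents do not give. For r between 0.3 and 0.7, the variance reduction is 9% to 49% against a day-30-only mean comparison and 35% to 15% against a change score. The patient equivalents of 99, 120 or 176 further assume complete EQ-5D data.

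The point does not extend to SSI. With about 11 expected events, adjustment would gain next to nothing, and the unadjusted comparison of proportions is a sound primary analysis for this pilot.

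**What to change.** Amend three sections together, so that they do not contradict one another:

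- **10.3.3:** take EQ-5D out of the general statement on proportions. State that the day-30 score is compared between arms by ANCOVA with treatment arm and pre-operative score as terms, reported as an adjusted mean difference with a 95% confidence interval.
- **10.5:** replace the present entry with a statement that adjustment is planned for EQ-5D only, using the pre-operative score, and that the SSI comparison is unadjusted.
- **10.8:** add a rule for a missing pre-operative score, for example imputing the mean baseline score of all randomised patients regardless of arm. Without this, the new analysis would sit beside a section that plans nothing for missing data.

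The cost is analysis-plan wording. Both scores are already collected, so no new data, visits or patients are needed. The one added burden is the missing-baseline rule. Reporting the observed SD and correlation alongside would also supply figures that the documents lack for planning the full study.

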### 10.6 Interim analysis and criteria for the premature termination of the trial

Not applicable

### 10.7 Subject population

Any subject randomised into the study that received at least one dose of study drug will be subjected to the study analysis.

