### 7.4 Blinding

The trial design is a single blinded trial. The trial participants will be blinded to their treatment.

Staff present at the time of operation, and prophylaxis, will be unblinded.

Health care staff not present at the time of operation will be blinded to treatment.

Outcome assessors will be blinded to treatment.

Final unblinding of all trial participants will occur after the creation of a locked analysis data set.

Medical/Anaesthetic notes will not contain the patient's treatment arm to limit unblinding.

Blinding of all care providers is not possible because of logistics relating to the blinding of treatments at short notice for all trial participants e.g. emergency surgery participants.

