### 7.9 Withdrawal criteria

The intervention is a single intervention, so withdrawal criteria are not expected to result from issues of being in the trial over a long period of time.

An acute event associated with the MP would therefore be the main medical reason for removal from the trial. An anticipated acute event e.g. recognition of allergy after enrolment, would also lead to removal from the trial. These cases should be discussed with a microbiologist to decide upon appropriate antibiotic prophylaxis if the surgical procedure is performed as planned. A microbiologist will want to know how much antibiotic has been administered prior to the allergy being recognised, and the expected duration of the procedure.

If withdrawn in this setting the participant would be included in the trial assessments as part of obtaining a complete data set for an intention to treat analysis.

Documentation to be completed on subject withdrawal (including recording reasons for withdrawal and any follow-up information collected with timing).

Withdrawn subjects are not to be replaced

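### Section 10.7 leaves randomised but undosed patients out of the analysis, while 7.9 keeps those withdrawn for allergy in an intention-to-treat data set; one as-allocated rule is needed

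*Combined protocol and SAP*

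**What the plan says.** Section 10.7 (Subject population) is the only place in section 10 that says who is analysed: "Any subject randomised into the study that received at least one dose of study drug will be subjected to the study analysis". It does not say that patients are analysed in the arm allocated, and it does not define *study drug*.

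Section 7.9 (Withdrawal criteria) names two reasons for removal. The first is drug-related: "An acute event associated with the MP would therefore be the main medical reason for removal from the trial". The second can arise before any drug is given: "An anticipated acute event e.g. recognition of allergy after enrolment, would also lead to removal from the trial". The section allows for the operation to go ahead with prophylaxis agreed with a microbiologist. A patient withdrawn in this setting is still to be "included in the trial assessments as part of obtaining a complete data set for an intention to treat analysis". No dosing condition is attached. The section ends: "Withdrawn subjects are not to be replaced".

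On knowledge of the arm, section 7.4 says: "Staff present at the time of operation, and prophylaxis, will be unblinded". Outcome assessors are blinded. Under 7.3.1 the envelope is opened once the decision to allocate has been made, and no limit is set on the time from randomisation to first dose.

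On the drugs, the trial summary names only cefuroxime as the medicinal product, whereas 8.1 lists cefuroxime and metronidazole for the comparator and again for the medicinal products. Under 8.6 both arms begin with intravenous cefuroxime: a fixed dose in the comparator arm, and a calculated loading dose followed by the infusion in the intervention arm.

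**The concern.** The surgical site infection (SSI) comparison is the stated primary outcome, and its denominator is described in two ways. A patient whose allergy comes to light after randomisation but before the first dose belongs to the intention-to-treat set under 7.9 and falls outside the analysis under 10.7. Section 10.7 also leaves out any other randomised patient who is operated on without study drug, for example because another antibiotic was used.

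A rule that requires at least one dose is easiest to defend when starting treatment cannot depend on allocation. That protection is missing here. The staff who give the drug know the arm, and the intervention needs a dose calculation and a programmed pump that the comparator does not. If non-starters differed between arms in number and in risk, the comparison would no longer be between the groups as randomised. With few events expected, a handful of exclusions could be visible in the result.

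The undefined term adds a second uncertainty: an infusion-arm patient given only a standard bolus might be counted or not, depending on who reads the rule.

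**Working it through.** **1. The two rules side by side, for randomised patients**

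| Patient | 7.9 | 10.7 |
|---|---|---|
| Acute event associated with the product (so dosed) | kept | kept |
| Allergy recognised after some drug was given | kept | kept |
| Allergy recognised before any dose, then operated on | kept | left out |
| Operated on without study drug for another reason | silent | left out |
| Infusion arm: loading dose given, infusion not started or interrupted | silent | kept |
| Infusion arm: standard bolus only | silent | depends on the meaning of study drug |
| Operation cancelled before any dose | silent | left out |

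The direct conflict is the third row. The fourth row is a gap in 7.9 and an exclusion under 10.7.

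**2. Does another section settle it?** No. Section 10.3.2 says only that proportions will be compared. Sections 10.5, 10.6 and 10.9 add nothing, and 10.8 plans no strategy for missing data. The CONSORT diagram in 10.3.1 would display exclusions but does not set the rule.

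**3. The plan's own figures (10.1)**

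- Pilot size: 60 patients with blood samples, about 30% not sampled. 60/(1 − 0.30) = 85.7, so 86. The stated 90 gives 90 × 0.70 = 63, which covers the 60 required, so 90 is a rounding up. Nothing below depends on it except the split.
- Arms: 90/2 = 45 each. This is an assumption, because simple 1:1 randomisation gives 45 only on average.
- Rates: 16.5% and 0.5 × 16.5% = 8.25%.
- Expected SSIs: 45 × 0.165 = 7.4 and 45 × 0.0825 = 3.7.

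**4. How far could exclusions move the SSI comparison?** Suppose there is no true effect (16.5% in both arms) and *k* patients are left out of the infusion arm only, each with SSI risk *q*. The remaining infusion-arm rate is (7.425 − *kq*)/(45 − *k*), and the risk ratio is that rate divided by 0.165. Both *k* and *q* are assumptions.

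| *k* | *q* | Infusion-arm rate | Risk ratio |
|---|---|---|---|
| 2 or 4 | 16.5% | 16.5% | 1.00 |
| 2 | 50% | 6.425/43 = 14.9% | 0.91 |
| 4 | 50% | 5.425/41 = 13.2% | 0.80 |
| 2 | 100% | 5.425/43 = 12.6% | 0.76 |
| 4 | 100% | 3.425/41 = 8.35% | 0.51 |

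At average risk there is no bias. If the same *k* and *q* applied in both arms, the formula would give the same rate in each and the ratio would stay at 1. The last two rows are the limiting case in which every excluded patient would have had an SSI.

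**5. How many such patients?** The documents give no rate. If a fraction *f* of 90 never starts, the expected number is 90*f* and the chance of at least one is 1 − (1 − *f*)^90. For *f* = 1%, 2% and 5% this gives 0.9, 1.8 and 4.5 patients, and chances of 60%, 84% and 99%.

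**6. Cost of keeping them.** Suppose the planned effect is real and *k* infusion-arm patients never start and run the comparator risk. The as-allocated rate is [(45 − *k*) × 0.0825 + *k* × 0.165]/45. For *k* = 2 it is (3.5475 + 0.33)/45 = 8.62%, risk ratio 0.52. For *k* = 4 it is (3.3825 + 0.66)/45 = 8.98%, risk ratio 0.54. The planned value is 0.50.

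**The case against.** The strongest reply is that the conflict is narrow and the mechanism weak. An acute event associated with the product implies a dose. Section 7.9 also asks how much antibiotic had been given when the allergy was recognised, so part of its allergy group is dosed too. It speaks of enrolment rather than randomisation, and allergy is screened beforehand. All of this stands, and it confines the direct conflict to undosed patients.

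A reader might infer that a pump that fails or is never programmed would remove an infusion-arm patient. It would not: the loading dose comes first, so that patient has received a dose. The product lists in 8.1 also make it natural to count an infusion-arm patient given only a standard bolus, although the protocol should say so.

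A reader might also infer that 10.7 hands unblinded staff the choice of who is counted. The documents allow starting to depend on the arm but do not show that it would. The decision precedes any SSI, and outcome assessors are blinded.

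Nor would the full study inherit a distorted estimate. Section 10.1 bases its sample size on a 50% reduction argued from ceftriaxone data and on a 16.5% control rate estimated from elective patients, not on the pilot's SSI ratio.

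Finally, the shifts in the table need exclusions from one arm only and risks well above 16.5%. That is true, and they are illustrations. None of these replies explains how a patient withdrawn before dosing is to be counted.

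**Conclusion.** The point holds in a limited form. Sections 7.9 and 10.7 cannot both be applied to a patient withdrawn after randomisation but before any dose. Section 10.7 also omits other operated patients who received no study drug, does not commit to analysis as allocated, and leaves its key term undefined. Following it as written would depart from the randomised comparison and from the protocol's own intention-to-treat statement.

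The likely number affected is small, because both arms start with intravenous cefuroxime. The size of any bias cannot be computed from the documents. It is nil if excluded patients have average risk. With no true effect, two to four infusion-arm exclusions at an assumed 50% risk would give a risk ratio of 0.91 to 0.80, on 45 per arm and the plan's 16.5%. What is exposed is the pilot's own SSI comparison; the full-study sample size is not affected.

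**What to change.** - In 10.7, state that the primary SSI analysis includes every randomised patient who has the operation, in the arm allocated, whatever prophylaxis was started, stopped or substituted.
- List patients whose operation does not take place, by arm, in the CONSORT diagram already planned. This is itself an exclusion after randomisation, so it should be visible.
- Keep the at-least-one-dose set for safety and pharmacokinetics, and define *study drug*, saying whether metronidazole alone, or a standard bolus in the infusion arm, counts.
- In 7.9, refer to the same rule and extend the follow-up statement to all operated patients who were never started. At present it covers only those withdrawn for an acute event or allergy, so follow-up of other non-starters should not be taken as already promised.

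The cost is a few sentences, follow-up of a few more patients by the existing procedures, and slight dilution of the estimated effect: from 0.50 to 0.52 or 0.54 with two or four infusion-arm non-starters, under the assumptions in step 6. No change to dosing or clinical management is involved.

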### 10.8 Procedure(s) to account for missing or spurious data

Strategies to maximise follow-up will be employed including telephone follow up and postal follow up  
No strategies are being planned for missing data.

### 10.9 Other statistical considerations.

None

### 10.11 Economic evaluation

None

## 11 DATA HANDLING

### 11.1 Data collection tools and source document identification

Data collection will be by paper case report forms (CRFs)

CRFs will be created to document

- Surgical history, including antibiotic prophylaxis and blood collection timings
- Day 5 surgical site infection assessment
- Post operative medical history including antibiotic consumption within 30 days of surgery, infection diagnoses and length of hospital stay
- End of study form including mortality data
- Quality of Life questionnaires (EQ5-D)
- Surgical site infection questionnaire.

Records of all participating patients (sufficient information to link records e.g., CRFs, hospital records and samples), all original signed informed consent forms and copies of the CRF pages will be kept.

Records will be stored in a locked room at the Old Medical School, Leeds General Infirmary, Leeds.

All research forms will be labelled with a patients study number.

To maximise data collection, telephone assessments and postal questionnaires will be used where patients are unable to attend in person for assessments.

### 11.2 Data handling and record keeping

- Data entry: Data will be added to an excel database stored on Leeds Teaching Hospitals NHS Trust.
- Data quality audit will be completed at the end of the study.
- Data will be stored on paper and online.
- Data will be pseudonymised.
- Data entry will be by a clinical researcher (clinical research nurse or research doctor)
- The PI will be responsible for data entry, quality and analysis.
- Arrangements to pseudonymise the data: Samples and data (case report forms) will be given a study number at the time of collection. A database linking study numbers to patients will be created and be separate to the data and samples. Both paper and electronic records will be kept as part of a data disaster recovery plan.

